11.3.4.2 Clinical Laboratory Evaluations

Summary statistics of laboratory variables will be calculated for each visit or study assessment by dose group. Shift tables of change from baseline will be provided.

11.3.4.3 Other Safety Evaluations

Summary statistics of vital signs, ECG, and height and weight variables will be calculated for each visit or study assessment by treatment group. The C-SSRS will be summarized by study visit by treatment group.

Anti-drug antibody assay results to WVE-003 will be described categorically. Summary statistics for anti-drug antibody titer results will be provided.

11.3.5 Analysis of Pharmacokinetic Variables

The plasma and CSF WVE-003 concentration, and potentially WVE-003-related metabolite data will be summarized for patients in the PK population. Excreted urine amount over each collection interval and the total amount over 24 hours will also be summarized.

For each patient in the PK population, the plasma WVE-003 concentration data will be analyzed by noncompartmental PK analysis. The parameters listed in [Table 9](#) will be determined. Additional PK parameters may be evaluated if deemed appropriate. Pharmacokinetic parameters for each dose group will be summarized for each WVE-003 dose level and each visit.

Table 9 Plasma Pharmacokinetic Parameters of WVE-003

Parameter	Definition
C_{max}	Maximum observed concentration
t_{max}	Time of occurrence of C_{max}
AUC_{last}	Area under the plasma concentration-time curve from time zero to the last quantifiable concentration

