2.2 Anticipated Benefit/Risk

Huntington's disease is a rare, progressive neurological disease¹. Currently available treatments for HD only mitigate symptoms and do not affect the underlying HD pathology, the disease course, or life expectancy after diagnosis of HD³². No approved treatments exist that can cure, slow, or reverse the course of HD. Based on the results of the nonclinical studies, WVE-003 has promise as a disease-modifying agent for the treatment of patients with HD. Target engagement was demonstrated both in vitro and in vivo. Nonclinical studies conducted in rats and monkeys yielded no toxicologically meaningful findings that would prevent initiation of clinical studies in HD patients.

[figure not shown]

2.3 Current Status of the Study and Dosing Paradigms as Recommended by the DEC and SMC

This is an adaptive study designed to evaluate data in an ongoing fashion to select and optimize dose levels and dosing frequencies. Data from Period 1 (SAD) have been reviewed by the DEC and SMC in accordance with [Section 4.4.1](#) and [Section 4.4.2](#), respectively, and recommendations were made regarding the number of cohorts, number of patients per cohort, and dose levels for Period 1 and P2C1.

In Period 1, the DEC/SMC have recommended dose escalation up to 90 mg. Initially, each cohort included 6 patients; however, due to variability in mHTT among patients, in , the DEC/SMC further recommended to expand each of the 3 single-dose cohorts to the cohort sizes listed below. Optional follow-up visits (up to 24 weeks postdose) were also added to provide the opportunity to obtain additional plasma and follow-up imaging samples prior to participation in Period 2. These additional data will be used to optimize the dose level:

- P1C1: 30 mg (n = 18; 2:1 active:placebo)
- P1C2: 60 mg (n = 18; 2:1 active:placebo)
- P1C3: 90 mg (n = 12; 2:1 active:placebo)

As of  the DEC/SMC recommended initiation of P2C1 with 30 mg administered Q8W through Week 16.

Subsequent dose levels, frequencies, number of cohorts, and number of patients per cohort will be determined based on DEC/SMC review of data from prior cohort(s) [REDACTED]

Section 4.4.1.3 [REDACTED]

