3 STUDY OBJECTIVES

Primary Objective:

- To evaluate the safety and tolerability of WVE-003 in patients with HD

Secondary Objectives:

- To characterize the PK of WVE-003 in plasma
- To characterize the concentration of WVE-003 in CSF

Exploratory Objectives:

- To evaluate the PD effect of WVE-003 on the levels of mHTT protein in CSF
- To evaluate the effect of WVE-003 on clinical measures of disease including the Unified Huntington's Disease Rating Scale (UHDRS) and Short Problem Behaviors Assessment (PBA-s)
- To evaluate the PD effects of WVE-003 on relevant biomarkers in CSF, plasma, and peripheral blood mononuclear cells (PBMCs) (e.g., levels of wtHTT protein, total huntingtin [tHTT] protein in CSF, and neurofilament light [NfL] in CSF and plasma)
- To evaluate changes from baseline in magnetic resonance imaging (MRI) of the brain

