4.1.4 Period 2 (Multiple-ascending-dose Period)

Period 2 will not be initiated until this Substantial Amendment to the IMPD with the supportive nonclinical data is approved by the local regulatory authorities. Following this approval, the Sponsor intends to initiate Period 2. The Sponsor will communicate this approval (in writing) directly to the study sites.

the DEC/SMC recommended that Period 2 can initiate at a dose level of 30 mg Q8W.

4.1.4.1 *Period 2 Assessment of Continued Patient Eligibility*

Before initiation of Period 2, the Investigator should confirm patient eligibility to continue in the study ([Section 4.2](#)). If any clinically significant medical findings are observed that, in the judgment of the Investigator (and in consultation with the Sponsor), would make the patient unsuitable for continued participation in the study and/or completion of the study procedures, the patient may not be allowed to participate in Period 2. Applicable evaluations and tests from the last in-clinic visit in Period 1 may be used if the last in-clinic visit occurred within 4 weeks prior to the Confirm Eligibility visit for Period 2. Patients who are considered eligible and have completed at least through Period 1 Week 12/Day 85 may participate in Period 2. New patients will be screened for eligibility.

4.1.4.2 *Period 2 Treatment Assignment*

Patients in P2C1 will receive 30 mg WVE-003 or placebo administered Q8W. Approximately 24 patients will be enrolled in P2C1. Dose levels and cohort sizes for Period 2 subsequent cohorts will be determined by the DEC/SMC, based on previous Period 2 cohort data. Doses will be administered no more often than Q8W through Week 16 (maximum of 3 doses). █

All patients from Period 1 will have the opportunity to roll into Period 2 and will receive up to 3 additional doses of WVE-003 or placebo. Patients will not be re-randomized and will continue to receive active drug or placebo based on Period 1 treatment assignment. Patients will roll into the current Period 2 cohort, irrespective of Period 1 dose level.

Patients may be replaced in accordance with the requirements for dose escalation. Future DEC/SMC recommendations may include the addition of new Period 2 patients. All new patients in Period 2 will receive up to 3 doses of WVE-003 administered no more often than Q8W.

4.1.4.3 *Period 2 Treatment*

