5.2.1.2 Highly Effective Methods of Contraception

Contraception methods that can achieve a failure rate of <1% per year when used consistently and correctly are considered highly effective birth control methods. Such methods are defined as one of the following:

- True abstinence, defined as refraining from heterosexual intercourse for the duration of the study, when in line with the preferred and usual lifestyle of the patient
- Vasectomized partner (if that vasectomized partner is the sole sexual partner and has received medical assessment of the surgical success of the vasectomy)
- An intrauterine hormone-releasing system (IUS).
- Combined (estrogen and progesterone containing) hormonal contraception associated with inhibition of ovulation (oral, intravaginal or transdermal combined)
- Progesterone-only hormonal contraception associated with inhibition of ovulation (oral, injectable, or implantable)
- An intrauterine device (IUD)

In addition, male participants must be required to use a condom, as contraception requirement, for the duration of the study and, at minimum, until 5 months (i.e., 5 elimination half-lives) after the last WVE-003 dose.

Note that periodic abstinence (calendar, symptothermal, post-ovulation methods), withdrawal (coitus interruptus), spermicides only, and lactational amenorrhoea are not acceptable methods of contraception.

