11.3.2 Analysis of Clinical Effects Endpoints

The change from baseline of the clinical effects endpoints will be analyzed using a mixed model for repeated measures (MMRM). The MMRM will include the relevant baseline measure and factor variables for time, dose group and time by dose group interaction. An unstructured variance-covariance matrix will be used to model the within-subject variability. If the MMRM with unstructured variance-covariance matrix does not converge, a compound symmetric structure will be used. Least square means of the time and dose group combinations and contrasts to placebo will be provided with 95% confidence intervals and p-values.

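### Period 2 PK summaries pool drug-naive entrants with rollovers dosed with 30, 60 or 90 mg as little as 12 weeks earlier, and the first-dose AUClast can mix 24 h and 6 h windows

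*Combined protocol and SAP*

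**What the plan says.** The secondary objectives (Section 3) are plasma PK and CSF drug level, the latter worded "To characterize the concentration of WVE-003 in CSF". Section 11.3 gives summary statistics by dose group and visit. For plasma parameters Section 11.3.5 adds: "Pharmacokinetic parameters for each dose group will be summarized for each WVE-003 dose level and each visit". Table 9 lists these as Cmax, tmax and AUClast.

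Period 1 tested 30, 60 and 90 mg, with planned cohorts of 18, 18 and 12 (Section 2.3). Rollovers keep their active or placebo assignment, and "Patients will roll into the current Period 2 cohort, irrespective of Period 1 dose level" (Section 4.1.4.2). P2C1 gives 30 mg at Weeks 0, 8 and 16. Rollover is allowed once the Period 1 Week 12/Day 85 visit is complete, which Section 4.1.3.2 treats as enough washout without giving a figure. Section 5.2.1.2 requires male participants to use condoms "until 5 months (i.e., 5 elimination half-lives) after the last WVE-003 dose".

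After the first Period 2 dose, plasma is sampled to 6 h in everyone and at 24 h in new patients only (Section 8.3, Table 4).

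For the exploratory endpoints, Section 11.3.2 states: "The MMRM will include the relevant baseline measure and factor variables for time, dose group and time by dose group interaction". The PD version drops the baseline term (Section 11.3.3). Section 11.3 sets the Period 2 baseline at the value before the first Period 2 dose for new and rollover patients alike. It adds a sensitivity analysis using the Period 1 baseline for rollovers. Both provisions cover PD and clinical endpoints, not PK.

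**The concern.** Dose group is not defined for Period 2 beyond the cohort dose. A table by dose group and visit therefore puts everyone on active drug in P2C1 into one 30 mg column. Nothing in the protocol separates PK by entry route, Period 1 dose or length of gap, or adjusts for drug already present before the first Period 2 dose.

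This bears on a secondary objective. Section 2.1 chose 30 mg Q8W partly to limit accumulation, and Section 2 says exposure and mHTT lowering will feed later dose and interval modeling. If predose and early trough levels contain drug from an earlier and sometimes larger dose, the pooled column overstates what 30 mg Q8W produces in its first interval and blurs any comparison of first-interval with later troughs. The unequal sampling after dose 1 is a second fault, and it does not depend on the half-life.

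**Working it through.** **Plan's own figure.** 3 doses × 30 mg = 90 mg, the P2C1 total in Section 2.1. An active rollover who completes P2C1 has received 30 + 90 = 120, 60 + 90 = 150 or 90 + 90 = 180 mg across the study.

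**Half-life and gap.** Section 5.2.1.2: 5 months / 5 = 1 month. The minimum gap is 12 weeks = 84 days (Section 2). With a month of 28, 30 or 30.44 days, 84 days is 3.00, 2.80 or 2.76 half-lives, leaving 12.5%, 14.4% or 14.8% of the dose.

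**Model (assumed).** Single-exponential decline with superposition, in mg-equivalents. D is the Period 1 dose and t the half-life.

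- Residual before Period 2 dose 1: R = D × 0.5^(84/t)
- Week 8 trough: T8 = (R + 30) × 0.5^(56/t), so the ratio to a naive patient is 1 + R/30
- Week 16 trough: T16 = (T8 + 30) × 0.5^(56/t)

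With t = 30 days, 0.5^(84/30) = 0.1436 and 0.5^(56/30) = 0.2742:

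| Period 1 dose | R | Week 8 trough | vs naive | Week 16 trough | vs naive |
|---|---|---|---|---|---|
| none | 0 | 8.23 | – | 10.48 | – |
| 30 mg | 4.3 | 9.41 | +14% | 10.81 | +3% |
| 60 mg | 8.6 | 10.59 | +29% | 11.13 | +6% |
| 90 mg | 12.9 | 11.77 | +43% | 11.45 | +9% |

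By Week 28 the excess is 1% to 2%.

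**Range on the half-life, 12-week gap.**

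- t = 15 days: 2.1% remains; Week 8 excess 2%, 4% and 6%; Week 16 excess under 1%.
- t = 45 days: 27.4% remains; Week 8 excess 27%, 55% and 82%; Week 16 excess 8%, 16% and 24%.

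**Longer gap, t = 30 days.** At 24 weeks, 0.5^(168/30) = 0.021, which is 0.6, 1.2 and 1.9 mg-equivalents, or 2%, 4% and 6% of one 30 mg dose.

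**Effect on a pooled mean (illustration).** The mix of new and rollover patients is not stated. If Period 1 filled to 18 + 18 + 12 = 48 and total enrollment were 54, at most 6 patients would be new. At least 18 of 24 in P2C1 (75%) would then be rollovers. The mean Period 1 dose is (18 × 30 + 18 × 60 + 12 × 90)/48 = 56.25 mg, and 56.25 × 0.1436 = 8.08. The pooled predose mean among active patients is 0.75 × 8.08 = 6.06, and the pooled Week 8 trough is (6.06 + 30) × 0.2742 = 9.89 against 8.23 in naive patients, or +20%. This assumes every rollover enters at exactly 12 weeks.

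**AUC window.** AUClast runs to the last quantifiable concentration (Table 9). On the dosing-day profile it can reach 24 h in a new patient but stops by 6 h in a rollover. The last dosing visit is also sampled only to 6 h in everyone, so even within new patients an AUClast ratio of last to first dose can compare unequal windows.

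**The case against.** The strongest replies concern scope.

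- The half-life comes from a contraception rule that names no matrix, while Section 4.1.3.2 regards 12 weeks as enough. This stands as a limit: the 30-day figure is an assumption, hence the range.
- Gaps longer than 12 weeks are expected, since Period 1 visits run to Week 24 and beyond while patients wait. This also stands; carryover then becomes small.
- The quoted sentence in 11.3.5 concerns Cmax, tmax and AUClast, and states no grouping for concentrations. However, Section 11.3 sets summary statistics by dose group and visit generally, so concentrations are pooled too. Cmax and tmax may be little affected; the documents give no concentrations to test this.
- Predose plasma and CSF samples on Period 2 Day 1 are already scheduled, so carryover will be measured. That makes the fix cheap; it does not separate the summaries.
- The SAP mentioned in Section 11.3.6 might define a split. It is not in the text supplied, and the protocol's rule pools.

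A reader might infer several stronger things that the documents do not support. Rollovers do not still carry 30 to 90 mg; that is what they were given. Period 2 levels do not as a whole fail to describe 30 mg Q8W: the distortion falls on predose and early trough values and fades by Week 16 to 28. Exposure-response modeling is not shown to be biased, because nothing says it will use pooled tables instead of individual levels and dosing histories. Nor are the MMRMs unprotected: Section 11.3 sets a Period 2 baseline and a Period 1-baseline sensitivity analysis. No passage shows that allocation differs by entry route.

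**Conclusion.** The point holds in a limited form. The stated rules produce a mixed Period 2 PK summary on a secondary objective. At the minimum 12-week gap and an assumed 30-day half-life, an active rollover starts Period 2 with 4.3 to 12.9 mg-equivalents, has a Week 8 trough 14% to 43% above a naive patient's, and a Week 16 trough 3% to 9% above. Across half-lives of 15 to 45 days the share of the Period 1 dose remaining is 2% to 27%; at a 24-week gap and 30 days it is about 2%. These sizes rest on single-exponential decline, on an implied half-life of unstated matrix, and on an unknown distribution of gaps. Placebo rollovers carry no drug. The mismatch of AUC windows after dose 1 rests on none of these assumptions.

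The modeling side is secondary. An entry-route term could adjust for separately randomized groups. A reader might take it as a correction for carryover, but carryover arises only in active rollovers and scales with Period 1 dose, so one main effect with 1 degree of freedom shared by placebo and active patients cannot remove it.

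**What to change.** In Section 11.3.5:

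1. Define dose group for Period 2, and summarize Period 2 plasma and CSF levels separately for new entrants and for rollovers by Period 1 dose.
2. Show the Period 2 Day 1 predose level for each of these groups.
3. Report a common 0-6 h AUC after dose 1.
4. Base statements on accumulation under 30 mg Q8W on new entrants.

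For the exploratory MMRMs (11.3.2, 11.3.3), entry route may be added as an adjustment alongside the sensitivity analysis in Section 11.3. If carryover is to be addressed, use a Period 1 dose term or a sensitivity analysis restricted to new entrants.

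The washout statement in Section 4.1.3.2 and the half-life figure in Section 5.2.1.2 must be reconciled, with the matrix named.

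The cost is extra table rows and no extra sampling. The downside is small subgroups: with only 6 new entrants, and 2:1 allocation assumed as in Period 1, accumulation would rest on 6 × 2/3 = 4 active patients. Individual values should then be shown beside the summaries.

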11.3.6 Interim Analyses

An unblinded interim analysis may be performed and the results summarized by dose group. The SAP will be finalized prior to the interim analysis.

An SMC ([Section 14.1](#)) will be assembled to review the safety, tolerability, PK, and PD activity. Unblinded statisticians or designees who will not be involved in the study conduct will generate and distribute the data to the SMC prior to each SMC meeting. Details on the safety assessments, frequency of review, meeting schedules, and controlled access to unblinded data are outlined in the SMC charter.

12 REGULATORY, ETHICAL, AND LEGAL OBLIGATIONS

12.1 Declaration of Helsinki

The Sponsor and Investigator(s) will ensure that this study is conducted in accordance with the most recent revision of the Declaration of Helsinki.

12.2 Good Clinical Practice

The study will be conducted according to the study protocol and SOPs that meet the guidelines provided by the International Conference on Harmonisation (ICH) for Good Clinical Practice (GCP) in clinical studies and any other applicable local regulatory requirements.

12.3 Institutional Review Boards/Ethics Committees

Federal regulations and ICH guidelines require that approval be obtained from an IRB or EC before participation of human patients in research studies. Before study onset, the protocol, ICF, and advertisements to be used for the recruitment of study patients and any other written information regarding this study to be provided to the patient must be approved by the IRB or EC. The documentation of all IRB/EC approvals and of the IRB/EC compliance with ICH guideline E6(R2): GCP will be maintained by the site and will be available for review by the Sponsor or its designee.

All IRB/EC approvals should be signed by the chairman or designee and should identify the IRB/EC name and address, the clinical protocol by title or protocol number or both, and the date of approval or when the favorable opinion was granted. The study protocol, appendices, and ICFs must be approved by the IRB/EC.

The Investigator is responsible for providing written summaries of the progress and status of the study at intervals not exceeding 1 year or otherwise specified by the IRB/EC. The Investigator must promptly supply the Sponsor or its designee, the IRB/EC, and, where applicable, the institution with written reports on any changes significantly affecting the conduct of the study or increasing the risk to patients.

12.4 Informed Consent Forms

Signed ICFs in compliance with the Declaration of Helsinki, current ICH and GCP guidelines, US Title 21 Code of Federal Regulations (CFR) Part 50, and applicable local regulations will be obtained from each patient before enrolling the patient in the study or performing any unusual or nonroutine procedure that involves risk to the patient.

Informed consent form templates will be provided by the Sponsor to investigative sites. If any institution-specific modifications to study-related procedures are proposed or made by the site, the ICF(s) must be reviewed by the Sponsor or its designee or both before IRB/EC submission. Once reviewed, the ICF(s) will be submitted by the Investigator to his or her IRB/EC for review and approval before the start of the study. If the ICF(s) is revised during the course of the study, all actively participating patients must sign the revised form.

Before Screening, each prospective patient will be given a full explanation of the study and be allowed to read the approved ICF. Once the Investigator is assured that the patient understands the implications of participating in the study, the patient will be asked to give consent to participate in the study by signing the appropriate ICF.

The Investigator will retain the signed original ICF(s) and give a copy of the signed original form(s) to the patient.

12.5 Privacy

The Sponsor and Investigator(s) will ensure that this study is conducted in accordance with the most recent version of the applicable privacy laws, including local privacy laws. Additional information on how the Sponsor handles privacy can be found at <https://wavelifesciences.com/privacy/>.

13 INVESTIGATOR'S OBLIGATIONS

The following administrative items are meant to guide the Investigator in the conduct of the study in accordance with GCP guidance. These items may be subject to change based on industry and government SOPs, working practice documents, or guidelines. Changes will be reported to the IRB/EC but will not result in protocol amendments.

13.1 Confidentiality

All laboratory specimens, evaluation forms, reports, and other records will be identified in a manner designed to maintain patient confidentiality. All records will be kept in a secure storage

area with limited access. Clinical information will not be released without the written permission of the patient, except as necessary for monitoring and auditing by the Sponsor, its designee, applicable regulatory agencies, or the IRB/EC.

The Investigator and all employees and coworkers involved with this study may not disclose or use for any purpose other than performance of the study any data, record, or other unpublished confidential information disclosed to those individuals for the purpose of the study. Prior written agreement from the Sponsor or its designee must be obtained for the disclosure of any said confidential information to other parties.

13.2 Investigator Documentation

Prior to beginning the study, the Investigator will be asked to comply with ICH E6(R2) 8.2 and Title 21 of the CFR by providing the following essential documents, including but not limited to the following:

- IRB/EC approval
- A fully executed Clinical Study Agreement
- Curriculum vitae for the Investigator and each sub-investigator listed on the IRB/EC application
- Financial disclosure information, as applicable
- IRB/EC-approved informed consent, samples of site advertisements for recruitment for this study, and any other written information regarding this study that is to be provided to the patient
- Laboratory certifications and normal ranges for any local laboratories used by the site

